Version 3 – 5/22/19

Study Title: *NEAT!2 Sedentary Behavior Reduction Intervention for Individuals with Past or Present Knee Symptoms, Injuries, or Surgeries**

Principal Investigator Name: [name]

NCT: 03987932

*Study stopped due to COVID-19 pandemic

A. SPECIFIC AIMS

The purpose of this proposed project is to conduct a randomized controlled trial to evaluate the effect of an mHealth sedentary reduction program (*NEAT!2*) over a 6 month period of time in adults with past or present knee symptoms, injuries, or surgeries. The specific aims of the project are:

Aim 1: To compare the change in sedentary behavior from baseline to 1 and 3 months between a smartphone app delivered sedentary reduction intervention with (*NEAT!2+Calls*) or without (*NEAT!2*) coaching calls and a delayed control (*Delayed NEAT!2*) in adults with past or present knee symptoms, injuries, or surgeries.

Aim 2: To examine the changes in physical function after participating in the *NEAT!2* or *NEAT!2+Calls* mHealth sedentary reduction interventions as compared to control from baseline to 1 and 3 months in adults with past or present knee symptoms, injuries, or surgeries.

Aim 3: To examine the maintenance in changes in sedentary behavior and physical function during the follow-up period between 3- and 6- months with no intervention contact in those who were initially randomized to *NEAT!2* or *NEAT!2+Calls*.

B. BACKGROUND AND SIGNIFICANCE

Sedentary behavior is defined as “any waking behavior characterized by an energy expenditure of ≤ 1.5 metabolic equivalents (METs) while in a sitting, reclining, or lying posture.”¹ Excess sedentary behavior is associated with numerous health consequences²⁻⁴ including poor physical function.⁵ Older adults with symptomatic knee pain spend the majority of waking hours engaged in sedentary behaviors.⁵ To reduce the risk of disability, improve quality of life, and prevent deterioration in physical function,^{6,7} it is critical to develop ways to decrease sedentary time. Several studies have started to explore preliminary ways to reduce sedentary time in older adults,⁸⁻¹⁰ however, to our knowledge, few studies have been done in older adults with current or past knee symptoms. Smartphone ownership among older adults is increasing and may provide a scalable opportunity to disseminate a sedentary reduction intervention. Therefore, this study aims to evaluate and compare changes in sedentary behavior between an mHealth sedentary reduction, mHealth intervention plus coaching, and delayed control group.

C. PRELIMINARY STUDIES

Using data obtained from the Osteoarthritis Initiative, we evaluated physical activity levels and sedentary behavior in adults with or at risk of developing knee osteoarthritis (KOA). Adults with KOA spend at least 2/3 of waking hours in sedentary behaviors.¹¹ We have found that greater amounts of time engaged in sedentary behaviors are associated with functional decline, lower quality of life, and weight gain.^{7,11,12} We have previously identified barriers and facilitators to physical activity in adults with KOA prior to having knee replacement. Barriers for activity included pain, physical limitations, and lack of motivation, whereas facilitators included having motivation to improve knee symptoms/outcomes, personal commitment to activity, and monitoring activity levels.¹³

Although this population is interested in being active, they are limited by knee pain. It is unclear how willing this population would be to decrease sedentary time, which may be a more feasible approach for those with knee pain. Additionally, those with end-stage KOA who recently had knee replacement are engaging in sedentary behavior ~69% of the day (manuscript in preparation).

Nine adults (53.1 ± 10.7 years, BMI $37.4 \pm 9.9 \text{ kg/m}^2$) with diabetes used the *NEAT!* app on 21.9 ± 8.0 days/month. *NEAT!* interrupted continuous bouts (≥ 20 minutes) of sitting by providing prompts on the smartphone to engage in light-intensity activity for ≥ 2 minutes. Prompts to interrupt sedentary time were given 5.8 ± 3.5 times/day. Participants reduced their sedentary time by $8.1 \pm 4.5\%$ (156.4 ± 75.0 min/day) between baseline and 1 month.¹⁴ Nearly 88% of participants indicated they would use *NEAT!* again in the future, suggesting high acceptability of the first iteration of the technology.

To inform the development of our *NEAT!*2 sedentary reduction intervention and update the *NEAT!* smartphone application, we surveyed 42 participants (61.8 ± 7.6 years, 67% female) on their beliefs about sedentary behavior and preferences for participating in a sedentary behavior reduction program. Nearly 80% of participants were located within the Columbia, SC region. Additionally, 88% of participants own a smartphone and 80% indicated they would be interested in participating in a sedentary reduction program.

D. RESEARCH DESIGN AND METHODS AND DATA ANALYSIS

Design Overview: This study is a three-group randomized controlled trial comparing changes in sedentary behavior between the *NEAT!*2 intervention with or without coaching calls and a control group in adults with past or present knee symptoms, injuries, or surgeries. A total of 90 participants will be randomized into one of three groups 1) *NEAT!*2 2) Delayed *NEAT!*2 or 3) *NEAT!*2+Calls. Data will be collected at baseline and months 1, 3, and 6.

Screening: Potential participants will complete an online screener to assess initial eligibility. Eligible patients will be invited to an in-person session where staff will review full details of the study and answer any questions. An equipoise induction will be conducted to review the pros and cons of being randomized to either condition to help prevent differential attrition.¹⁵ Interested and eligible participants will provide informed consent, approved by the University of South Carolina's Institutional Review Board. Participants will complete the baseline assessment and wear an accelerometer for 7 days. Participants will need to have 4 valid days of accelerometer data to be eligible for randomization. They will not receive any feedback on sedentary time and will be encouraged to engage in typical behavior during this period. In addition, to ensure compatibility and eliminate the potential of technological issues following randomization, all participants will download a test version of *NEAT!*2 app on their phone. The test version of *NEAT!*2 app will remain idle, and participants will not receive notifications about their sedentary time until after randomization.

Randomized Conditions:

- 1) **NEAT!2:** *NEAT!2* is guided by the Dual-Process Theory¹⁶ and targets both automatic and controlled processes.¹⁷ Participants randomized to *NEAT!2* will have their *NEAT!2* app turned on after randomization. Using the smartphone's internal accelerometers, *NEAT!2* detects periods of movement vs. non-movement. When 30 minutes of continuous non-movement or sedentary time is detected, the *NEAT!2* app will initiate a reminder notification via vibration or audio as well as display a reminder on the phone's lock/home screen. This novel approach will take advantage of the frequent number of times an individual looks at his/her phone.¹⁸ If and when the app detects activity/movement, the 30-minute timer will restart; thus, the app will only provide notifications when prolonged bouts of inactivity are objectively detected. Further, the app will only trigger notifications during participants waking hours. Each notification will consist of a different message. Participants will be asked to use the app for the 3 months of the intervention. Participants will be given an initial goal to reduce total sedentary time by 30 minutes/day, ultimately progressing to a 90 minute/day reduction by 3 months. After the 3-month assessment, participants randomized to *NEAT!2* will have the option to continue using the app until 6 months.
- 2) **Delayed NEAT!2:** Participants randomized to the delayed control condition will not receive any contact or app between baseline and 3 months. However, after completing the 3-month assessment, participants in the delayed condition will receive the *NEAT!2* application. Participants will then have the option to use the app between 3 and 6 months.
- 3) **NEAT!2+Calls:** *NEAT!2+Calls* participants will have their *NEAT!2* app turned on after randomization. In addition, to receiving the identical app and given the same goals as participants randomized to *NEAT!2*, *NEAT!2+Calls* participants will receive bi-weekly coaching calls. Coaching calls will be completed by trained coaches, be semi-scripted, and last approximately 10-15 minutes. During calls, coaches will use motivational interviewing techniques, discuss goal progression and educational handouts, problem solve, and set a SMART (specific, measurable, attainable, realistic/reward, timely) goal related to reducing sedentary time. All calls will be recorded and timed to allow the assessment of treatment fidelity. After the 3-month assessment, participants randomized to *NEAT!2+Calls* will have the option to continue using the app until 6 months. During this time, participants will not receive any coaching calls.

Treatment Fidelity: Telephone sessions will be audiotaped, and a 15% sample rated for treatment fidelity on a quarterly basis. If fidelity falls below 80%, coaches will be retrained. Fidelity checklists will assess intended session content (e.g., app usage, SMART goal setting). [name] will train the coaches on the intervention and will oversee the fidelity evaluation. Coaches will meet with [name] once a month to review treatment delivery.

Assessments: Participants will be asked to complete four in-person assessments at baseline, 1 month, 3 months, and 6 months. All in-person assessments will take place

at the TecHealth Center at the University of South Carolina ([name]) and each session will be last approximately 45 minutes in length. Table 1 provides an overview of what outcomes will be assessed, how they will be assessed, and at what time points.

Table 1. Study Outcomes and Measures				
Concept	Variable	Measure	Data Collection	Time Points
Aim 1 Outcomes				
Sedentary Behavior	Objectively measured sedentary behavior	Sitting minutes/day and Sitting bouts >30 minutes during waking hours	ActivPal worn on thigh for 7 days for 24 hours/day	0, 1, 3, & 6 months
	Daily diary	Times monitor on/off, awake/sleep	Paper log for 7 days	0, 1, 3, & 6 months
Aim 2 Outcomes				
Physical Function	Objectively measured physical function	Timed up and go; 30-second chair stands, 6-minute walk test based on OARSI recommended procedures ¹⁹	In-Person Assessment	0, 1, 3, & 6 months
Demographic, Health Status, and Process Variables				
Demographics	Age, Sex, Race, Ethnicity, Marital Status, Education	Demographic Questionnaire	REDCap survey	0 (baseline)
Health Status	Height, Weight, Waist Circumference BMI	Stadiometer, electric scale, and tape measure	In-Person assessment	0, 1, 3, & 6 months
	Medical History	Brief medical history	REDCap Survey	0 (baseline)
Knee Symptoms	Self-reported knee symptoms	Knee injury and Osteoarthritis Outcome Score (KOOS) ²⁰	REDCap Survey	0, 1, 3, & 6 months
	Pain intensity, pain interference, & mobility	Patient-Reported Outcomes Measurement Information System (PROMIS) ^{21,22}	REDCap Survey	0, 1, 3, & 6 months
Habit Strength	Self-reported habit strength	Adapted Self-Report Habit Index ²³	REDCap Survey	0, 1, 3, & 6 months
Domain specific sedentary behavior	Self-reported	Total sitting time and domain specific sitting time	SIT-Q ²⁶ and the Sedentary Behavior Questionnaire ²⁷	0, 1, 3, & 6 months
Behavioral Beliefs	Self-reported beliefs on	TPB Survey ²⁴ and Elicitation Interview ²⁵		0, 1, 3, & 6 months

Personal Environment Changes	physical activity and sedentary behavior Self-reported change in use of activity monitor	Physical Activity Monitor Changes Questionnaire	REDCap Survey and In-Person Interview REDCap Survey	(interview only 0 months) 1, 3, & 6 months
------------------------------	---	---	--	---

Primary Outcomes:

- Sedentary behavior will be measured using ActivPAL™ (PAL Technologies Ltd, Glasgow, UK), a small lightweight (15 g) uni-axial accelerometer. The time spent sitting/lying, standing, and stepping. The ActivPAL summarizes data in 15 second intervals over 24 hours at a sampling frequency of 10 Hz.²⁴ During assessments, participants will be asked to wear the ActivPAL on their thigh for 7 days. The monitor will be secured to the participants leg with medical grade waterproof adhesive tape. Participants will also be asked to complete a log indicating times the ActivPAL was worn and taken off over the 7-day assessment period in addition to what times they went to sleep and woke up.

Secondary and Exploratory Outcomes:

- Physical function measures will include the chair stand, timed up and go, and 6-minute walk test. All physical function tests will be completed following Osteoarthritis Research Society International (OARSI) recommendation procedures.¹⁹ During the chair stand test, patients are asked to complete as many chair stand repetitions as possible during a 30-second period. The Timed Up and Go Test assesses the time in seconds taken to rise from a chair, walk 3-meters, turn, walk back to the chair, and sit down. The Six Minute Walk Test evaluates the maximal distance a patient can cover during a 6-minute period.
- Knee symptoms will be assessed using the Knee Injury and Osteoarthritis Outcome Score (KOOS).²⁰ Participants will self-report on symptoms, stiffness, pain, daily function, and active function of their knee from the past week. Patient-Reported Outcomes (pain intensity, pain interference, and mobility) will be assessed using Patient-Reported Outcomes Measurement Information System (PROMIS).²¹ PROMIS utilizes a computer adaptive test via RedCap.²⁵
- Adapted Self-Report Habit Index²³ assesses habit strength related to sitting. Participants answer the questions on a 1-7 Likert scale ranging from “Strongly Disagree” to “Strongly Agree”.
- Sedentary behavior will also be assessed with the SIT-Q.²⁶ This will be assessed as part of the web screening to estimate how many hours individuals spent sitting on an average day. The survey assesses time spent sleeping and sitting time during multiple domains (e.g., meals, transportation, work, leisure). The survey will also be administered at each assessment to explore changes in domain specific sedentary time. The Sedentary Behavior Questionnaire²⁷ will also be assessed to examine specific activities done while sitting (9 behaviors such as TV watching, reading, and using the phone on weekends vs. weekdays).

- Participants' control, normative, and behavioral beliefs toward sedentary behavior and physical activity will be assessed with (1) a modified Theory of Planned Behavior (TPB) survey²⁴ - The survey includes 37 questions about the participants' beliefs towards sedentary behavior and physical activity utilizing a 1-7 Likert scale. (2) An elicitation interview modified from Speed-Andrews et al.²⁵ will be administered at baseline. The interview contains 12 open-ended questions and elicits participants' beliefs related to sedentary behavior and physical activity.
- Waist Circumference will also be assessed as a predictor of abdominal visceral fat. Measurement will be done twice during expiration, taking the average for analyses, by positioning an anthropometric tape midway between the palpated iliac crest and the palpated lowest rib margin in the mid-axillary lines (smallest part of the waist).

Evaluation: Following completion of the 3 or 6 month assessment, participants will be asked to complete a short evaluation form asking about their feelings and attitudes regarding the NEAT!2 program and the NEAT!2 application. The evaluation will aid in future research utilizing the *NEAT!2* application or research directed at reducing sedentary behavior in this population.

Statistical Analysis: Baseline participant characteristics will be described. Mixed ANCOVA's will be conducted to examine differences in sedentary behavior, physical function, and patient-reported outcomes across time by group. Additionally, we will control all sedentary time analyses for moderate intensity physical activity. All analyses will be performed using SAS 9.2 and SPSS.

E. PROTECTION OF HUMAN SUBJECTS

1. TARGET POPULATION:

We will aim to recruit 90 participants from Columbia, SC and surrounding areas. The target population will consist of adults over the age of 40 who identify with past or present knee pain, injury, or surgery.

Inclusion criteria: Eligible participants will 1) be at least 40 years of age, 2) own an Android or iOS smartphone, 3) have their smartphone near them (in their pocket, in their hand, or within 10 feet of them for >50% of their waking day) 4) be willing to download the study application on their smartphone and have the application be compatible with their device, 5) spend at least 7 hours/day sitting, assessed by the SIT-Q, 6) have at least 4 days of valid accelerometer data at baseline, 7) have knee pain (at least one knee with pain, aching, or stiffness on most days for one month of the last 12 months), knee injury, or knee replacement within the last 5 years, and 8) read, speak, and understand English.

Exclusion criteria: Participants will only be excluded if they 1) have any contraindications to activity, 2) have a mobility limiting comorbidity (e.g. spinal stenosis), or 3) have a scheduled surgery (i.e., total knee replacement) within the next 6 months.

2. RECRUITMENT PLANS:

We will target recruitment channels including: 1) promotions in publications with low or no advertising cost (i.e., Craig's List); 2) electronic and social media recruitment blurbs (i.e., Facebook, Twitter, website, email newsletter, electronic billboard, etc.); 3) posting flyers around USC campus area and local Columbia businesses, health centers, rehabilitation or orthopedic centers; 4) word of mouth; and 5) emails to individuals from previous studies who expressed interest in participating in future trials.

All recruitment material will list study eligibility criteria and requirements and include a phone number, email address, and website where participants can reach staff if they have any general questions regarding study participation.

3. EXISTING DATA/SAMPLES:

Not applicable

4. CONSENT/ASSENT:

Written informed consent will be obtained in person. Full disclosure will be made of the nature and potential risks of participating in the study. Prior to starting, all participants will be asked if they have any questions about their participation to ensure they understand the procedures. The consent form has been developed according to the requirements of the University of South Carolina Institutional Review Board. All participants will receive a copy of their signed consent form. A copy of all signed IRB-approved consent forms will be kept in a locked file.

5. POTENTIAL RISKS:

Risks associated with interrupting sedentary time with brief bouts of light-intensity physical activity such as standing or light ambulation are minimal. Participants may experience skin irritation from wearing the activPAL accelerometer for 7 days at each assessment. In the event the participant experiences skin irritation, we will ask the participant to remove the device. We will provide them with additional tape, with multiple options available to accommodate individual reactions and preferences to medical grade tape, to reaffix to the other leg.

6. POTENTIAL BENEFITS:

Participants may or may not directly benefit from participating in this study, however the risks of participating in either randomized group are considered minimal. Participants may gain skills and knowledge regarding how to decrease sedentary behavior.

Participants who are adherent to the intervention and reduce sedentary time may have greater reductions in pain and improvements in physical function. If the intervention is acceptable, safe, and effective, it may provide an innovative approach to reduce sedentary time among adults with previous or past knee symptoms, injuries, or surgeries.

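### The plan does not say how the baseline outcome enters the mixed ANCOVA; read naturally, it gives a valid change-score contrast that is less precise than a baseline-adjusted one

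*Combined protocol and SAP*

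**What the plan says.** The model statement in section D, Statistical Analysis, is one sentence: "Mixed ANCOVA's will be conducted to examine differences in sedentary behavior, physical function, and patient-reported outcomes across time by group". The next sentence supplies the only named covariate: "Additionally, we will control all sedentary time analyses for moderate intensity physical activity". No covariate is named for physical function or the patient-reported outcomes, and the role of the baseline outcome is not stated for any outcome.

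Aim 1 in section A is "To compare the change in sedentary behavior from baseline to 1 and 3 months between a smartphone app delivered sedentary reduction intervention", with or without coaching calls, and a delayed control. Aim 2 asks the same of physical function over the same visits. Aim 3 concerns maintenance "during the follow-up period between 3- and 6- months with no intervention contact in those who were initially randomized to" the two app arms.

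The baseline outcome is available. Under Screening, "Participants will complete the baseline assessment and wear an accelerometer for 7 days", and four valid days are needed before randomisation. Table 1 lists the function tests at month 0 as well. On size, the Design Overview says "A total of 90 participants will be randomized into one of three groups", and the title block adds "Study stopped due to COVID-19 pandemic".

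**The concern.** Read together, a time-by-group analysis and an aim framed as change from baseline suggest that baseline is the first level of time, with each arm's baseline mean estimated freely. With complete data, the group-by-time contrast at a visit is then the difference between arms in mean change. This gives the baseline value a weight of exactly one, whatever its correlation with follow-up. A baseline-adjusted analysis estimates that weight from the data and is more precise unless the best weight happens to be one.

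What is at stake is precision. Ninety participants in three arms is about 30 per arm if allocation is equal (the ratio is not stated). The study was stopped, so the arms may be smaller; the documents give no enrolment count. Precision that needs no further data is worth having in that setting.

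**Working it through.** The plan gives no power calculation, alpha, effect size or standard deviation to go with the 90, so there is no figure of its own to reproduce. The check therefore compares the two analyses.

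**Inputs.** Correlation r between baseline and follow-up: not in the documents, assumed 0.5 to 0.9. Equal arms, 30 each: assumed from 90/3. Complete data: assumed. Let s be the baseline standard deviation and k the ratio of follow-up to baseline standard deviation.

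**Variance per participant.**
- Change score: s²(1 + k² − 2rk).
- Baseline-adjusted: s²k²(1 − r²).
- Difference: s²(1 − rk)². This is never negative, so adjustment does not lose precision apart from about one degree of freedom.

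**Equal standard deviations (k = 1).** The ratio of change-score to adjusted variance is 2(1 − r)/(1 − r²) = 2/(1 + r).

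| r | 2/(1+r) | Change-score arm size matching 30 adjusted |
|---|---|---|
| 0.5 | 1.33 | 40.0 |
| 0.8 | 1.11 | 33.3 |
| 0.9 | 1.05 | 31.6 |

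A simulation with three arms of 30 gave ratios of 1.32 at r = 0.5 and 1.04 at r = 0.9, in line with the formula.

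**Unequal standard deviations.** The gain vanishes when rk = 1. At r = 0.8 and k = 1.25, the change-score variance is 1 + 1.5625 − 2.0 = 0.5625 and the adjusted variance is 1.5625 × 0.36 = 0.5625 (in units of s²), a ratio of 1.00. At r = 0.8 and k = 0.8 they are 0.36 and 0.2304, a ratio of 1.56.

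**Illustration in power.** The only standard deviation of change in the documents is 75 min/day (section C, nine adults with diabetes, baseline to 1 month). Take a difference of 60 min/day, the midpoint of the 30 and 90 min/day participant goals and not a planned effect, with two-sided 5% alpha and k = 1. The adjusted standard deviation is 75 × √((1 + r)/2): 65.0 at r = 0.5, 71.2 at 0.8 and 73.1 at 0.9. Noncentral t power for one pairwise contrast, with one degree of freedom removed for the covariate:

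| Per arm | Change score | Adjusted, r = 0.9 | r = 0.8 | r = 0.5 |
|---|---|---|---|---|
| 30 | 86% | 88% | 89% | 94% |
| 20 (assumed) | 69% | 71% | 74% | 81% |

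These powers are illustrative only. Section C pairs a reduction of 156.4 min/day with 8.1%. If the percentage is relative to baseline, baseline would be 156.4/0.081 ≈ 1,931 min/day, more than the 1,440 minutes in a day. The variance ratio does not depend on that standard deviation.

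**The case against.** The strongest reply is that the plan never says baseline is a level of time. It applies the ANCOVA label to function and patient-reported outcomes without naming any covariate for them, so an unstated baseline covariate may have been intended. This stands: the documents establish that the role of baseline is unstated, and the change-score analysis is the natural reading, not a stated fact.

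A second reply is that Aim 1 asks about change and the group-by-time contrast answers it. That also stands. A reader might infer that the planned test is invalid or biased; under randomisation it is neither.

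Third, the ratios rest on assumed correlations and equal standard deviations, and the calculations leave out the moderate-activity covariate. The gain beyond that covariate is not assessed, and a ratio of 1.00 is possible. This limits the claimed size, but not the direction of the comparison between the change-score and adjusted analyses.

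A reader might also count chance baseline imbalance carried into the change score as a second harm. It is the same loss: with k = 1, 2(1 − r) = (1 − r²) + (1 − r)², and the last term is the imbalance contribution.

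**Conclusion.** The point holds as a low-cost gain in precision, conditional on baseline being a level of time with free arm means. On that reading the change-score variance exceeds the adjusted variance by 5% to 33% for r from 0.9 to 0.5 with equal standard deviations. It can exceed it by more, or not at all, when the standard deviations differ. The correlations are assumed, and the min/day and power figures should not be cited as properties of this trial.

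Two wider readings are not supported. First, Table 1 lists two sitting measures and Aim 1 two visits without naming a lead, and a reader might call this part of the same error. It is missing detail, and choosing a lead is a trade-off. In an illustration with 30 per arm and a standard deviation of change of 75, where both app arms are 60 and then 30 min/day below the delayed arm, an adjusted joint test at month 3 has 36–43% power (r from 0.8 to 0.5), against 82% for group-by-time over months 0, 1 and 3. Second, a reader might infer that month 6, after the delayed arm has been given the app, enters the between-arm comparison. Aims 1 and 2 stop at month 3 and Aim 3 is confined to the two initial app arms, so the documents already settle this.

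**What to change.** In the Statistical Analysis paragraph, state for Aims 1 and 2 that the month 1 and month 3 values are modelled with arm, visit, arm-by-visit and the baseline value of the same outcome as covariate. Keeping baseline as an outcome, with one mean common to all arms, would serve equally. If a baseline covariate was always intended, one sentence saying so is enough.

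The cost is a few sentences, about one degree of freedom and no new data. For sitting time no randomised participant is lost, because four valid baseline days are a condition of randomisation. For the function tests no completeness rule is stated, so the same cannot be promised for Aim 2.

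Because the study has stopped, the choice should be made before outcome data are analysed; if they have been analysed already, it should be labelled post hoc. The sponsor may also wish to name a lead Aim 1 measure and visit, but that is an optional clarification and not part of this correction.

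### All sedentary-time analyses are adjusted for moderate-intensity activity with no time point, no measure and no analysis without it; if visit-level values are used, Aim 1 no longer estimates the total effect on sitting

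*Combined protocol and SAP*

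**What the plan says.** Section D, Statistical Analysis, plans mixed ANCOVAs to "examine differences in sedentary behavior, physical function, and patient-reported outcomes across time by group" and then adds: "Additionally, we will control all sedentary time analyses for moderate intensity physical activity". Nothing else in the paragraph qualifies the covariate. It gives no time point and plans no unadjusted or sensitivity analysis.

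Aim 1 in section A is "To compare the change in sedentary behavior from baseline to 1 and 3 months" between the app with calls, the app without calls, and the delayed control. Table 1 gives the device outcomes as "Sitting minutes/day and Sitting bouts >30 minutes during waking hours", collected at 0, 1, 3 and 6 months.

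No measure of moderate activity is defined. Table 1 has no row for its amount. Under Primary Outcomes the ActivPAL is described with the words "The time spent sitting/lying, standing, and stepping"; that sentence is incomplete and should not be taken as a full list, but no intensity threshold appears. The survey under Secondary and Exploratory Outcomes asks about "beliefs towards sedentary behavior and physical activity utilizing a 1-7 Likert scale", which is attitude and not amount. The other activity item in Table 1 records changes in activity-monitor use.

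Aim 3 concerns maintenance from month 3 to month 6 "with no intervention contact in those who were initially randomized to" one of the two app groups. Under Randomized Conditions, "after completing the 3-month assessment, participants in the delayed condition will receive the" app.

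**The concern.** The Aim 1 estimate depends on a choice that the plan does not state. Moderate activity measured at baseline cannot have been changed by the app. Moderate activity measured at 1 or 3 months can have been, and every minute of it is a minute not spent sitting. Adjusting for it removes whatever part of the app's effect works by turning sitting into moderate activity. The result answers a different question: how much sitting changes at a given level of moderate activity. Because the covariate applies to all sedentary-time analyses, no planned analysis would return the total effect if the visit-level reading were followed.

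The same rule reaches the sedentary-behaviour part of Aim 3, where visit-level adjustment would turn maintenance into maintenance net of activity change. With the delayed group given the app after month 3, there is no untreated comparison there, so the matter is only which quantity is estimated. Physical function is not affected, because the covariate is confined to sedentary time.

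**Working it through.** The plan gives no figure to reproduce: it states no effect size, design SD or power. The check is of the mechanism, with an illustration of scale.

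**Inputs from the documents.** Participant goals of 30 and 90 min/day (Randomized Conditions), used only as a scale and not as expected effects.

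**Assumed inputs.** The slope *b* (change in sitting per extra minute of moderate activity), from -0.5 to -1.5. The share *s* of the sitting reduction that becomes moderate activity, at 0, 5 and 10%. Neither is in the documents.

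**Formula.** If *E* is the total reduction in sitting, the arm difference in moderate activity is *s* × *E*, and the visit-level adjusted estimate is *E* × (1 - |*b*| × *s*). The loss is |*b*| × *s* × *E*, shown at *b* = -1 with the range for -0.5 to -1.5 in brackets:

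| Share *s* | Loss from 30 min/day | Loss from 90 min/day | Loss as % of effect |
|---|---|---|---|
| 0% | 0 | 0 | 0 |
| 5% | 1.5 (0.75–2.25) | 4.5 (2.25–6.75) | 5 (2.5–7.5) |
| 10% | 3 (1.5–4.5) | 9 (4.5–13.5) | 10 (5–15) |

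**Simulation of change scores.** 30 per arm (equal split of 90 assumed), 3,000 runs, SD of change 75 min/day (the nine-person pilot in section C), *b* = -1, activity SD 15 min/day assumed, true reduction 90 min/day.
- No arm difference in activity: 89.8 unadjusted, 89.7 with baseline activity, 89.7 with visit-level activity.
- Arm difference of 5 min/day (5/90 = 5.6%): 90.4, 90.4 and 85.3. The formula gives 90 - 5 = 85 for the last.

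**Simulation of a three-arm repeated-measures ANCOVA.** Months 1 and 3 as outcomes, baseline sitting as a covariate, 150,000 per arm. Assumed: 960 waking minutes; moderate activity mean 30, SD 15; light activity or standing mean 300, residual SD 60. Month-3 estimates for a true 90, with visit-level activity in the model (formula value in brackets):

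| Fitted slope | *s* = 0% | *s* = 5% | *s* = 10% |
|---|---|---|---|
| -0.39 | 90.0 | 88.4 (88.2) | 86.5 (86.5) |
| -0.80 | 89.7 | 86.6 (86.4) | 82.8 (82.8) |
| -1.21 | 89.7 | 84.4 (84.6) | 78.9 (79.1) |

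The fitted slopes are shallower than the -0.5, -1 and -1.5 built into the data. At a 5% share the loss is therefore 90 - 88.4 = 1.6 to 90 - 84.4 = 5.6 min/day, or about 2 to 6% of the effect. Without the covariate, or with baseline activity in its place, estimates were 89.7 to 90.4 throughout.

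With 30 per arm, the 5% case gave 86.6 on average. The simulated standard error was about 13 to 14 min/day under these assumed SDs, so the shift of about 90.0 - 86.6 = 3.4 is roughly a quarter of a standard error.

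**Not sized.** The bouts outcome; the contrast between the app with and without calls (both arms have the same goals, so the 30 and 90 scale says nothing about it); and Aim 3.

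**The case against.** The strongest reply is that the sponsor probably means a baseline value. In a classical between-within ANCOVA a covariate usually takes one value per person, so that reading is at least as natural as the visit-level one, and it is harmless. This stands, though it does not settle the matter: mixed-model software also accepts time-varying covariates, the model runs across time, and the monitor is worn at every visit.

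The second reply is that the interruptions are light. Section C describes the earlier app as prompting light-intensity activity, and section E.5 speaks of standing or light ambulation. This largely stands, and it is why shares of 0 to 5% fit best. It is not conclusive: the first describes a previous version, the second is a risk statement, and in this trial's app any detected movement restarts the timer whatever its intensity.

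A reader might infer that the plan does adjust the primary analysis for a post-randomisation variable, that the result is therefore biased toward no effect, or that a large part of the effect would be lost. The documents support none of these. Visit-level use is not stated. The direction depends on whether the app raises or lowers moderate activity, which the documents do not say, and shared causes of activity and sitting could also move the estimate. A large loss would need much of the sitting reduction to become moderate activity, which no section suggests.

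The title page says the study stopped because of the pandemic, so the number analysed is unknown. Whatever data exist still need one defined main analysis.

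**Conclusion.** The point holds as an ambiguity in the primary analysis that should be fixed; it is not a demonstrated bias. Three things are plain on the page: no restriction to baseline, no defined measure, and no analysis without the covariate. The missing measure matters under either reading.

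If visit-level values are used, the estimand for Aim 1 changes whatever the size of the numerical shift. That size cannot be derived from the documents. On the assumption that 0 to 5% of the sitting reduction becomes moderate activity, the simulated loss is about 0 to 6% of the effect (up to 7.5% by formula at the steepest assumed slope). The 10% row is illustration only. These figures concern sitting minutes in the app-versus-delayed contrast and rest on the assumed slopes, shares and SDs. Confidence is medium, because the sponsor's intended reading is not known.

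**What to change.** Replace the covariate sentence with:

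> The primary analyses of sedentary time (daily sitting minutes and sitting bouts longer than 30 minutes) compare groups at 1 and 3 months, adjusted for the baseline value of the same outcome. Moderate-intensity activity measured after randomisation is not a covariate in these analyses or in the Aim 3 analysis of sedentary behaviour; any model that adjusts for it is labelled exploratory.

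The second sentence is the essential one. The first makes the Aim 1 contrast explicit for both device outcomes; it does not imply that a group-by-time model is wrong in itself. Baseline moderate activity may stay as a covariate, provided its instrument and threshold are fixed before analysis.

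The cost is two sentences of analysis-plan wording and no new data. The sponsor gives up the activity-adjusted estimate as the main result and keeps it as exploratory.
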